6 STRUCTURE AND METHODOLOGY OF STATISTICAL ANALYSIS

6.1 Descriptive Statistics

Categorical variables will be summarized with counts (n) and percentages (%). For continuous variables, the number of non-missing observations (n), mean, standard deviation (SD), standard error (SE) of the mean, 95% confidence interval (CI) of the mean, median, first (Q1) and third (Q3) quartiles, minimum (min) and maximum (max) will be tabulated.

The 95% confidence interval for continuous data will be calculated using the normal approximation. If less than 30 patients with non-missing data are available (in a sub-group, if applicable) for a specific continuous data point, no confidence interval will be reported for this data point.

The 95% confidence interval for proportions will be calculated using the exact Clopper-Pearson method.

When applicable, summaries will be provided by visit of assessment.

6.2 Level of Statistical Significance

No statistical inferences will be performed for this study. Confidence intervals (CIs) will be two-sided with 95% coverage.

6.3 Baseline

Unless otherwise specified, baseline value will be defined as the last non-missing assessment prior to the first study treatment dose dosing on Day 1 (including unscheduled and repeat assessments). If the last non-missing assessment is performed on the same date as the first study treatment administration and time is not available, the assessment will be considered as baseline, except for adverse events (AEs) not related to a pre-dose assessment and medications starting on the first study treatment dose administration date which will be considered post-baseline.

6.4 Interim Analysis

No interim analyses are planned.

6.5 Reference Start Date and Analysis Day

Analysis day will be calculated from the first study treatment dose administration date and will be used to show start/end day of assessments or events.

Analysis day = (Date of event – Date of first dose administration) + 1 if date of event is on or after the date of first dose administration of study treatment;

= (Date of event – Date of first dose administration) if date of event is before the date of first dose administration of study treatment.

In the situation where the assessment/event date is partial or missing, analysis day will be missing.

6.6 Software Version

All analyses will be performed using SAS® software Version 9.4 or higher.

7 DATA HANDLING

7.1 Missing Data

No imputation will be made for missing data. See [Appendix 2](#) for handling of completely or partially missing dates and time for prior and concomitant medications and adverse events.

7.2 Computation of Derived Variables

Change from baseline will be calculated as:

Assessment value at post-baseline Visit X – Baseline value.

Percent change from baseline (%) will be calculated as:

$$(\text{Assessment value at post-baseline Visit X} - \text{Baseline value}) / \text{Baseline value} * 100.$$

Percent change from baseline will be missing in situation where baseline value equals to 0.

7.3 Windowing Conventions

Windowing conventions will apply to all local tolerability, hypopigmentation, hyperpigmentation and scarring, and AK lesions count assessments.

Visits will be analyzed as scheduled. Scheduled, unscheduled, and early termination visits measurements will only be included if the scheduled, early termination, or unscheduled measurement falls within the analysis visit windows as described in [Table 2](#).

Table 2 Analysis Visit Windows

Analysis Visit	Target Study Day	Local tolerability, Hypopigmentation, hyperpigmentation and Scarring, AK lesions count
Baseline	Refer to Baseline definition	Refer to Baseline definition
Day 5	5	[1 post-dose; 5]
Day 8	8	[6; 11]
Day 15	15	[12; 22]
Day 29	29	[23; 43]
Day 57	57	[44; EOS]

If there is more than one assessment for a given analysis visit, the assessment closest to the target day will be considered. If two assessments fall at the same distance from the target day for a given analysis visit and one of them is a scheduled assessment, the scheduled assessment will be considered. If two assessments fall at the same distance from the target day for a given analysis visit and none of them is a scheduled assessment, the first assessment will be considered.

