### 10.3.3 Unscheduled and Repeated Tests

#### Unscheduled Tests

As deemed necessary by the Investigator, additional safety test(s) can be performed at any time during the trial in order to follow-up the progress of any clinically relevant abnormal finding, investigate any potential new adverse event, etc. These additional tests outside of the initial schedule of the trial will be considered "unscheduled tests" and will not be associated with any trial visit.

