7.4 Repeated or Unscheduled Assessments

When repeated measurements are done, the repeated measurement will be considered for the windowing and analysis in lieu of the original measurement.

For local tolerability, hypopigmentation, hyperpigmentation and scarring, and AK lesions count assessments, unscheduled and early termination assessments will be remapped as mentioned in [section 7.3](#). All data from visits will be listed under the nominal visit, and the analysis visit will also be presented if it differs from the nominal visit.

For other assessments, unscheduled measurements will not be summarized in by-visit summary tables or figures. Early Termination (ET) visit assessments will be summarized as part of the Day 57/ET visit. All data from unscheduled and early termination visits will be listed.

M-14867-32

Statistical Analysis Plan Status: Version (17 Jan 2023)

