14.1 Local Tolerability Assessment

Local tolerability is assessed based on the review of the following signs in the treatment field: erythema, flaking/scaling, crusting, swelling, vesiculation/pustulation, and erosion/ulceration and will be evaluated both individually and as a composite score (total of the 6 individual scores ranging from 0 to 18). These signs will be graded as: 0=absent, 1=mild (slightly, barely perceptible), 2=moderate (distinct presence), and 3=severe (marked, intense). If one or more individual score is missing, the composite score will be set as missing.

The maximum local tolerability signs composite score across visits will be derived as the maximum local tolerability assessment (LTA) composite score observed post-baseline for a patient. The maximum local tolerability of individual signs across visits will be derived as the maximum LTA of an individual sign observed postbaseline for a patient.

Descriptive statistics will be presented for local tolerability signs composite score by visit, and for maximum local tolerability signs composite score across post-baseline visits. Frequency and percentages by visit of patients presenting any individual and composite local tolerability signs and associated CI based on exact Clopper-Pearson method will be presented. The presence of any individual and composite local tolerability sign is defined by a score of >0. Frequency and percentages by visit for specific local tolerability individual signs results and maximum local tolerability of individual signs across post-baseline visits will also be provided.

The 95% CI will be presented for the median of the maximum local tolerability composite score.

Figures presenting the number of patients with each local tolerability individual sign (absent/mild/moderate/severe) by visit, and a figure presenting the mean local tolerability composite score by visit will be produced.

The time to maximum LTA score for each individual sign and the time to maximum LTA composite score will be calculated as the time (in days) from the first dose of study treatment to the time of the first occurrence of the maximum LTA score observed post-baseline for each individual sign and composite score, respectively. That is, for each individual sign, time to maximum LTA, in days, will be calculated as follows:

(Date of first post-baseline occurrence of maximum LTA score for an individual sign – Date of first dose)

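### The SAP does not say whether the maximum local tolerability scores are taken before or after one-record-per-window selection; if after, peak reactions can be understated

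*SAP*

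**What the plan says.** SAP 7.3 sets its own scope: "Windowing conventions will apply to all local tolerability, hypopigmentation, hyperpigmentation and scarring, and AK lesions count assessments". Each analysis visit then receives one record. The rule is "If there is more than one assessment for a given analysis visit, the assessment closest to the target day will be considered". A scheduled record takes precedence only in a tie: "If two assessments fall at the same distance from the target day for a given analysis visit and one of them is a scheduled assessment". Around Day 8 the window runs from Day 6 to Day 11.

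SAP 7.4 sends extra tolerability scores through the same rule: "unscheduled and early termination assessments will be remapped as mentioned in" Section 7.3. It adds that, where a measurement is repeated, "the repeated measurement will be considered for the windowing and analysis in lieu of the original measurement". For all other types of assessment, 7.4 confines its exclusion of unscheduled values to by-visit outputs. No such limit is written for local tolerability.

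SAP 14.1 says: "The maximum local tolerability signs composite score across visits will be derived as the maximum local tolerability assessment (LTA) composite score observed post-baseline". Single signs are treated alike: "The maximum local tolerability of individual signs across visits will be derived as the maximum LTA of an individual sign observed postbaseline for a patient". Time to maximum runs from the first dose to the date on which that maximum was first seen. A patient whose maximum remains 0 is censored at the last score.

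Protocol 10.3.3 allows unscheduled assessments: "additional safety test(s) can be performed at any time during the trial in order to follow-up the progress of any clinically relevant abnormal finding".

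**The concern.** Read together, these sections leave the order of two steps undefined. One programmer may select one record per window and then take the maximum. Another may take the maximum over everything recorded after baseline. Both can cite the SAP. The selection rule looks only at distance from the target day, so under the first reading a severe score can be discarded in favour of a milder one a day or two away.

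Safety and tolerability are the primary objective. Maximum score and time to maximum, by sign and composite, are listed safety endpoints. SAP 14.1 otherwise reports sign frequencies by visit, so the maximum-score table is the planned summary that shows how many patients ever had a sign. The sample size rationale (SAP 5) rests on percentages of that kind: 90% with any sign, 8% with vesiculation/pustulation and 12% with erosion/ulceration. Protocol 5.1.5 reports that composite scores peaked at Day 8 in the Phase 3 trials and around Day 7 to 8 in the 100 cm² trial, so the window that matters most is the one covering Days 6 to 11.

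**Working it through.** The plan states no figure for this point, so there is nothing to reproduce. The check applies the SAP rules to constructed score sequences.

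**Inputs.** Windows from SAP 7.3, Table 2: Day 5 = Day 1 post-dose to 5; Day 8 = 6 to 11; Day 15 = 12 to 22; Day 29 = 23 to 43; Day 57 = 44 to end of study. These have no gaps, so up to the end of study a score is lost only through selection within a window. Time to maximum = date of first maximum minus date of first dose, so a score on Day d gives d − 1 days. All scores below are invented. In cases A to C the later scheduled composites are 3, 1 and 0 at Days 15, 29 and 57.

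**Direction.** Window-selected records are a subset of all records. The maximum of a subset is equal to or lower than the maximum of the whole.

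**Cases.**

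- A. Day 5 = 4, Day 8 = 9 (both scheduled), unscheduled Day 11 = 12. Distances in the Day 8 window: |8 − 8| = 0 and |11 − 8| = 3, so Day 11 is dropped. All records: maximum 12 at 11 − 1 = 10 days. After selection: maximum 9 at 8 − 1 = 7 days.
- B. Scheduled Day 5 = 4, unscheduled Day 8 = 7, scheduled visit held on Day 10 = 9 (inside the ±2 day allowance). Distances 0 and |10 − 8| = 2, so the scheduled score is dropped. All records: 9 at 9 days. After selection: 7 at 7 days.
- C. Unscheduled Day 3 = 10, scheduled Day 5 = 4, scheduled Day 8 = 9. Distances in the Day 5 window: |3 − 5| = 2 and |5 − 5| = 0, so Day 3 is dropped. All records: 10 at 2 days. After selection: 9 at 7 days.
- D. One sign, grade 2 at an unscheduled Day 11 and 0 at every scheduled visit including Day 8. Day 11 is dropped as in A. The maximum becomes 0, the patient no longer counts as ever having the sign, and time to maximum is censored.

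The maximum falls in all four cases. Time to maximum shortens in A and B (10 to 7 days, 9 to 7 days) and lengthens in C (2 to 7 days).

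**Size, on assumptions only.** Let p be the true any-time percentage and q the share of affected patients whose every positive score sits on a dropped record. Reported percentage = p × (1 − q). The documents give no value for q.

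| Assumed q | p = 8% | p = 12% |
|---|---|---|
| 0 | 8.0% | 12.0% |
| 5% | 7.6% | 11.4% |
| 10% | 7.2% | 10.8% |
| 25% | 6.0% | 9.0% |

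For the mean maximum composite, the shift is −(share of patients affected × points lost). For example, 0.05 × 3 = 0.15 points lower, or 0.20 × 6 = 1.2 points lower. These shares are also assumed.

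**The case against.** The best defence is that SAP 14.1 already means all records. It speaks of the highest score observed after baseline for a patient, and it computes time to maximum from actual dates and not from analysis visits. The protocol endpoint covers all visits. The closest-to-target rule is worded for a given analysis visit, and SAP Table 3 explains the remapping as a way to reduce gaps in tables. On this reading the bias is zero. In addition, every tolerability score is listed, and Protocol 10.5.2.1 requires an adverse event report for any sign that interrupts or ends dosing or needs concomitant medication.

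Much of this stands. A reader might infer that the SAP specifies a downward-biased derivation, but it does not: it permits one. A reader might also assume that dropped unscheduled scores are usually the worst. The protocol allows such tests to follow the course of a finding, which includes confirming that it is resolving. Nor is a Day 5 visit held a day late an ordinary route of loss: that visit has no time window and may not be skipped, so a late one is a deviation.

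The defence does not close the gap. The scope of 7.3 is all local tolerability assessments, and 7.4 writes a by-visit limit for other data but not for these. SAP 14.1 also describes the maximum as taken across visits, and the only visits defined for analysis are the windowed ones. Listings and adverse event tables do not correct the maximum-score table.

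**Conclusion.** The point holds as an unresolved ambiguity with a conditional effect. If the maximum is taken after window selection, the maximum score and any-time incidence can be understated and cannot be overstated. A case is lost from the incidence only if the sign scores 0 on every retained record; losing a worse grade alone lowers the maximum but not the count. Time to maximum has no fixed direction, so a general claim that all peak-reaction endpoints shift downward would go too far. The loss is not confined to unscheduled scores, as case B shows. The size is unknown, because the number of extra assessments and their severity are not in the documents; the figures above are illustrations. The change is still worth making, since it removes a choice on a primary-objective safety endpoint at almost no cost.

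**What to change.** Add to SAP 14.1 that maximum score, time to maximum and any-time presence, for each sign and for the composite, use all post-baseline assessments: scheduled, unscheduled, early termination and follow-up. Add to SAP 7.3 that the one-record-per-window selection applies only to by-visit tables and figures.

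The addition must fit the repeat rule in 7.4, or a new ambiguity arises. State that an original measurement replaced by a repeat stays out of the maximum only where the repeat was made because of a problem with the first test, which is the post-baseline ground for repeats given in Protocol 10.3.3.

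The cost is a few sentences in the SAP and the matching derivation in the programs. No new data are collected, and the by-visit outputs do not change.

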7.4 Repeated or Unscheduled Assessments

When repeated measurements are done, the repeated measurement will be considered for the windowing and analysis in lieu of the original measurement.

For local tolerability, hypopigmentation, hyperpigmentation and scarring, and AK lesions count assessments, unscheduled and early termination assessments will be remapped as mentioned in [section 7.3](#). All data from visits will be listed under the nominal visit, and the analysis visit will also be presented if it differs from the nominal visit.

For other assessments, unscheduled measurements will not be summarized in by-visit summary tables or figures. Early Termination (ET) visit assessments will be summarized as part of the Day 57/ET visit. All data from unscheduled and early termination visits will be listed.

M-14867-32

Statistical Analysis Plan Status: Version (17 Jan 2023)

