3.2 Trial Design

This is a Phase 3, multicenter, open-label, single-arm trial to evaluate safety and local tolerability of tirbanibulin ointment 1% administered topically for 5 days over a field of approximately 100 cm² on the face or balding scalp in adult patients with actinic keratosis (AK). The study consists of a 4-week (28-day) Screening Period, a 5-day Treatment Period, and a Response Assessment Period of approximately 7 weeks (see [Table 1](#), Schedule of Assessments):

- During the Treatment Period, patients will apply tirbanibulin ointment 1% once daily for 5 days beginning on Day 1.
- All patients will be evaluated for safety, tolerability, and the presence of AK lesions in the treatment field (TF) until completion of the Response Assessment Period at Day 57.

Enrollment will be controlled such that the trial population is representative of the population expected to use the product in terms of age and treated area. A minimum of 50% of patients older than 65 years old will be included and approximately two-thirds of the patients will be treated for AK lesions on the face and one-third on the scalp.

M-14867-32

Statistical Analysis Plan Status: Version (17 Jan 2023)

Table 1 Schedule of Assessments

Period	Screening*	Treatment		Response Assessment				
Visit(s)	1	2	At home, once-daily self-administration ^m	3	4	5	6	7
Day(s)	-28 to -1	1 (Baseline)	2 to 5	5	8	15	29	57
Visit Time Window (days)	None	None		None	±2	±2	±3	±3
Informed consent	X							
Inclusion & exclusion criteria	X	X ^a						
Demographics	X							
Medical/surgical history	X							
AK history/AK treatment history	X							
Prior and concomitant medications/therapies	X	X ^a		X	X	X	X	X
Fitzpatrick skin type	X							
Treatment field identification ^k	X	X ^a						
Vital signs ⁱ	X	X ^a						X

M-14867-32

Statistical Analysis Plan Status: Version (17 Jan 2023)

Period	Screening*	Treatment		Response Assessment					
		1	2	At home, once-daily self-administration ^m	3	4	5	6	7
Visit(s)									ET/EoS
Day(s)	-28 to -1		1 (Baseline)	2 to 5	5	8	15	29	57
Visit Time Window (days)	None	None			None	±2	±2	±3	±3
Physical examination ^d	X								X
Clinical chemistry, hematology, urinalysis	X								X
ECG ^b	X								X
Pregnancy test for WOCBP ^c	X	X ^a							X
Study App installation and instructions		X ^a							
Study App review by Investigator ⁱ					X				
Study drug application		X	X						
Instructions for self-administration and study drug dispensing		X							
Study drug return					X ^e				

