14.4 Clinical Laboratory Parameters

Laboratory parameters of hematology, blood chemistry, and urinalysis will be summarized using descriptive statistics at baseline and at subsequent visits. Change from baseline values will be presented for each post-baseline assessment. Frequencies and percentages for each result will be provided for qualitative urinalysis data.

In addition, shift tables (for hematology, blood chemistry, and quantitative urinalysis: low-normal-high at baseline versus low-normal-high at follow-up in a 3-by-3 contingency table; for qualitative urinalysis: normal-abnormal at baseline versus normal-abnormal at follow-up in a 2-by-2 contingency table) will be provided to assess changes in laboratory values from baseline. Only patients with a baseline result and a result at the specified post-baseline visit for the parameter will be considered in the shift tables.

Separate listings of all data for hematology, blood chemistry, and urinalysis will be provided. In addition, separate listings of data for hematology, blood chemistry, and urinalysis will be provided for each parameter where a patient had at least one clinically significant or not clinically significant abnormal result.

A listing will be provided for Pregnancy test results.

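### Laboratory, ECG and vital-sign summaries rest on one post-baseline value (Day 57/ET), so an abnormality seen only on an unscheduled test, resolved by then and not reported as an AE, reaches listings only

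*SAP*

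**What the plan says.** The schedule of assessments (SAP 3.2, Table 1; the protocol has the same table) marks the row for "Clinical chemistry, hematology, urinalysis" at Screening and Day 57 only. The ECG row is the same. Vital signs add a pre-dose measurement on Day 1.

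SAP 7.4 remaps unscheduled values to analysis visits for local tolerability, pigmentation, scarring and lesion counts. It treats everything else differently: "For other assessments, unscheduled measurements will not be summarized in by-visit summary tables or figures". For those same assessments, "Early Termination (ET) visit assessments will be summarized as part of the Day 57/ET visit", and "All data from unscheduled and early termination visits will be listed".

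Protocol 10.3.3 explains why unscheduled safety tests are done: "in order to follow-up the progress of any clinically relevant abnormal finding, investigate any potential new adverse event".

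SAP 14.4 to 14.6 plan descriptive statistics, changes from baseline and shift tables at baseline and post-baseline visits. For the laboratory shifts, "Only patients with a baseline result and a result at the specified post-baseline visit for the parameter will be considered in the shift tables"; vital signs and ECG have an equivalent rule. SAP 15.2 plans no further analyses.

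**The concern.** Change from baseline in laboratory data and other safety assessments is a named safety endpoint (SAP 4.2.1) under the primary objective. Treatment lasts five days and the only scheduled look afterwards is at Day 57. Apart from an ET visit, any laboratory, ECG or vital-sign result between dosing and Day 57 must come from an unscheduled test. Those are the results nearest to exposure, and they are requested because something is suspected. SAP 7.4 keeps them out of the only summaries planned for these domains.

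At stake is whether the report can state, with a count and a denominator, how many patients had an abnormal value at any time after dosing. Protocol 5.1.5 reports that systemic exposure rose in proportion when the ointment was applied to 100 cm², so the question is a fair one for this trial.

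**Working it through.** No figure in the plan needs reproducing. The check is a reading of the rules, a day count and one illustration.

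**1. Scheduled values per domain (Table 1)**

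| Domain | Scheduled pre-dose | Scheduled post-dose |
|---|---|---|
| Laboratory | Screening | Day 57/ET |
| ECG | Screening | Day 57/ET |
| Vital signs | Screening, Day 1 | Day 57/ET |

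Each domain has exactly one scheduled post-baseline value.

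**2. Distance from dosing.** With the last dose on Day 5, the value for a completer falls 57 − 5 = 52 days later. The ±3-day window gives 54 − 5 = 49 to 60 − 5 = 55 days.

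**3. A patient with an abnormal unscheduled value between Day 1 and Day 57.** The shift table depends only on the Day 57/ET result:

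- Day 57/ET normal: classified normal post-baseline.
- Day 57/ET still abnormal: classified abnormal.
- No Day 57/ET result: not in the shift table.

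In the first and third cases the abnormal value enters no laboratory, ECG or vital-sign summary.

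**4. Other routes into the tables**

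- *Baseline.* SAP 6.3 lets an unscheduled pre-dose result serve as baseline. This does not help after dosing.
- *Repeats.* Under SAP 7.4, "the repeated measurement will be considered for the windowing and analysis in lieu of the original measurement". Protocol 10.3.3 allows repeats for a technical problem with a test, or at screening to confirm eligibility. A post-dose test done for cause is neither.
- *Adverse events.* Protocol 10.5.1.1 requires abnormal results that the investigator considers clinically significant to be recorded as AEs. Section 10.7.3 adds post-dose abnormalities that are clinically relevant, need an intervention or a diagnostic test, or may end treatment. These reach the TEAE tables of SAP 14.3.
- *Listings.* All unscheduled values are listed. SAP 14.4 to 14.6 add separate listings of patients with any abnormal result, clinically significant or not.

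What is left is an abnormality that is seen only on an unscheduled test, is not abnormal at Day 57/ET and is not reported as an AE. The planned shift tables are meant to catch such values: laboratory shifts use low, normal and high whatever the clinical significance, and vital-sign and ECG shifts have their own category for abnormal but not clinically significant.

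**5. Illustration.** The documents give no rate. Assume 100 patients, all with baseline and Day 57/ET results, of whom x have such an abnormality, with nobody else abnormal after dosing. Exact (Clopper-Pearson) 95% limits, the method named in SAP 6.1, are the 0.025 quantile of Beta(x, n − x + 1) and the 0.975 quantile of Beta(x + 1, n − x). For x = 0 the upper limit is 1 − 0.025^(1/100) = 3.6%.

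| x | Day 57 shift table | Worst post-baseline shift |
|---|---|---|
| 1 | 0% (0 to 3.6) | 1% (0.0 to 5.4) |
| 3 | 0% (0 to 3.6) | 3% (0.6 to 8.5) |
| 5 | 0% (0 to 3.6) | 5% (1.6 to 11.3) |

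**The case against.** The strongest reply is that the plan already handles the findings that matter. A marked abnormality found for cause would ordinarily meet the AE criteria and be counted as a TEAE by SOC, preferred term, severity and relationship. Everything else is listed, and listings for about 100 patients in one arm can be read. SAP 7.4 also follows the protocol, which does not attach unscheduled tests to a visit (10.3.3) and asks for normal and abnormal counts at scheduled visits (11.8.1). A worst-value table has its own weakness: only patients tested for cause contribute extra values, so it mixes incidence with intensity of testing.

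Most of this stands, and it rules out some stronger readings.

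- A reader might infer that unscheduled values are kept out of every table. The rule covers by-visit summaries only; the baseline and AE routes remain open.
- A reader might infer that abnormal values are counted as normal. Nothing is recoded: patients are classified by their actual Day 57/ET result, or left out if there is none.
- A reader might infer that the SAP contradicts the protocol, or that the Day 57 tables give biased estimates. They describe Day 57/ET and do not claim to estimate occurrence at any time.

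The reply does not close the remaining gap. The AE route depends largely on the investigator's opinion, and values outside range but not clinically significant will generally not take it. A listing supplies no count or denominator. Agreement with the protocol is no bar to an added table, and a worst-value shift needs no visit assignment. SAP section 16 already departs from the protocol's rule on unscheduled tests, to reduce missing data in the tables.

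Pooling ET results with Day 57 is a lesser matter. It places an early result under a late label, but it does bring that result into the table.

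**Conclusion.** The point holds as a narrow reporting gap, not an error or a contradiction. In three safety domains the summaries describe a single time about 52 days after the last dose for completers. A transient abnormality found for cause and not reported as an AE is visible only in listings.

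The size cannot be stated from the documents, which give neither a rate of unscheduled testing nor a share of abnormal results reported as AEs. The 1 to 5 per 100 above is an assumption that shows scale and is no evidence that the gap will be filled. The conclusion rests on the schedule in Table 1, the wording of SAP 7.4, and the absence from SAP 14.4 to 14.6 and 15.2 of any worst-value or any-time summary. It does not touch local tolerability, on which the sample size is based and for which unscheduled values are remapped into the analysis. It merits a cheap improvement.

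**What to change.** Keep the by-visit tables as planned. Add to each of SAP 14.4, 14.5 and 14.6 one supplementary shift from baseline to the worst post-baseline value, as follows:

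- Use all scheduled, unscheduled and ET results after baseline, and state where the period ends.
- Take as denominator the patients with a baseline and at least one post-baseline result. This brings back a patient who has an unscheduled result but no Day 57/ET value.
- For two-sided parameters, such as laboratory tests with low and high limits, show the lowest and the highest value in separate panels.
- Add a footnote that unscheduled tests are done for cause, so extra values come only from patients in whom something was suspected.

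Record the addition in SAP section 16. Showing early ET results on their own line instead of under Day 57/ET is optional.

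The cost is SAP wording and one extra panel per domain; no new data are needed, since SAP 7.4 already requires these values to be listed. The drawbacks are slightly less favourable abnormal counts and the selective nature of for-cause testing. Both are small when the panel stands beside the by-visit tables and does not replace them.
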